Smoking, Sex Hormones and Pregnancy Study Protocol

[figure not shown]
Version: 12.0
Version Date: 6.2.2016

SIGNIFICANCE

Women and Smoking. Compared to men, women are at an increased risk for both smoking-related morbidity and mortality, as well as smoking relapse.¹⁻⁶ Women respond less favorably to smoking cessation treatment and, on average, quit smoking at an older age than men.²⁻³ Women of childbearing age are of particular concern given the short-term and long-term risks associated with pregnancy such as placental previa, restricted fetal growth, sudden infant death syndrome, and, later in the child's life, attention-deficit disorder and overweight/obesity.⁷⁻⁹ More than 90% of women who quit smoking during pregnancy relapse shortly after delivery, resulting in the continuation of smoking-related risks well after delivery as mothers are the primary source of secondhand smoke (SHS) exposure for offspring.¹⁰ SHS contains more than 50 carcinogens, as well as other toxins. Children exposed to SHS have increased risk of respiratory and ear infections, and miss more days from school.¹¹ To date few, if any, interventions have addressed potential biological and/or neurobiological causal mechanisms associated with the sex differences in risk for smoking relapse. *In sum, effective smoking cessation interventions for women of childbearing age are lacking, perhaps due to a limited understanding of the causal pathways involved in smoking relapse.*

Sex Hormones & Drug Abuse Behavior. The evidence for the role of sex hormones on drug abuse behaviors is growing. The animal literature provides strong evidence indicating that progesterone is protective against drug abuse behaviors whereas estrogen promotes drug abuse behaviors.¹²⁻¹³ The clinical literature is less clear but recent work provides support for this theory. For example, one of our recent studies, utilizing a randomized prospective design, observed better smoking cessation outcomes among those women who quit smoking during the luteal phase (low estradiol/high progesterone) compared to those who quit in the follicular phase (high estradiol/low progesterone).¹⁴ Further support comes from a second study that also observed improved smoking cessation outcomes among those with a quit date in the luteal phase compared to the follicular phase while using bupropion as a smoking cessation aid.¹⁵ However, discordant results come from two additional studies. These studies observed improved smoking cessation outcomes in the follicular phase rather than the luteal phase.^{16, 17} In addition to differences in methodology, one of the primary differences between these four studies is that the first two^{14, 15} did not use nicotine replacement therapy whereas the second two did.^{16, 17} These data ultimately prompted a hypothesis suggesting that the timing of a quit attempt during the menstrual cycle and the pharmacotherapy used may be equally important in determining success of a quit attempt,¹⁸ indicating nicotine response may be a factor that needs to be addressed. Relatedly, there is a growing body of animal literature to support that a metabolite of progesterone – allopregnanolone – acts as a potential protective factor.¹² Allopregnanolone is a neuroactive steroid which increases the release of dopamine and has been shown to be associated with behavioral effects of alcohol in a non-dependent sample of women, as well as withdrawal symptoms in a sample of dependent women.^{19, 20} One theory is that withdrawal symptom severity, and therefore risk for smoking relapse, may be associated with changes in dopamine release. This may be one of the mechanisms involved with these observed associations between sex hormones and smoking relapse. *Increasing evidence exists indicating that the sex hormones influence addictive behaviors and sex hormones are known to change dramatically during pregnancy. However, to our knowledge, no study to date has investigated the association between sex hormones and smoking during pregnancy.*

Sex Hormones & Pregnancy. Levels of progesterone, allopregnanolone, and estradiol all change dramatically during pregnancy (**Figure 1**). Progesterone is produced mainly from the corpus luteum during early pregnancy, then by the placenta in mid- to late-pregnancy. Levels of progesterone vary widely among women but levels generally increase from approximately 10 ng/ml in the first trimester up to 200 ng/ml in the third trimester.²¹ Similarly, allopregnanolone increases by ten-fold during pregnancy.²² Estradiol, primarily from the ovaries, increases from 2 to 18 ng/ml during pregnancy.²¹ Given that the literature indicates that progesterone is protective against drug abuse behaviors whereas estradiol facilitates these behaviors, the ratio between these two hormones may be of critical importance. During pregnancy, the estradiol/progesterone (E2/P) ratio can decrease from 0.20 to 0.09.²¹ *In brief, while all three sex hormones increase during pregnancy,*

[figure not shown]

the sex hormones that may be protective against drug abuse behaviors (progesterone, allopregnanolone) increase more dramatically than the sex hormone that may facilitate drug abuse behaviors (estradiol); this results in the ratio to shift in favor of those hormones that are protective, possibly offering an overall protective effect against drug abuse behavior during pregnancy.

Formulation of Central Hypothesis. Pregnancy provides an ideal clinical model for testing our central hypothesis given the literature to-date indicates the following: (1) while pregnancy is the most common time for women to quit smoking, the majority are unable to sustain smoking abstinence after delivery,⁷ (2) sex hormones increase during pregnancy, with progesterone increasing the most dramatically,²¹ and (3) progesterone and allopregnanolone appear to be protective against drug abuse behaviors.¹² Therefore, *our central hypothesis is that higher levels of progesterone and allopregnanolone, along with lower estradiol/progesterone ratios, will be associated with a favorable change in smoking-related symptomatology and nicotine response.*

INNOVATION

This project incorporates at least three highly innovative aspects. First, this study will be among the first to systematically investigate the role of sex hormones on smoking-related symptomatology and nicotine response during pregnancy. This information will directly improve the state of the scientific knowledge by filling a gap in the literature and potentially offering a new direction in smoking cessation and relapse prevention interventions. For example, if progesterone proves to be associated with a reduction in smoking-related symptomatology during pregnancy, treatment of exogenous progesterone may facilitate cessation and help prevent relapse. Delivery of exogenous progesterone during the third trimester is an accepted treatment for pre-term delivery prevention;²³ therefore investigation into the delivery of exogenous progesterone as a smoking cessation treatment during times of high risk for relapse (such as immediately prior to delivery and/or in the post-partum period) would be warranted. Further, this type of treatment may extend beyond the pregnant population, to non-pregnant women, who are at an increased risk for relapse compared to their male counterparts.² Second, to our knowledge no studies to date have investigated the role of allopregnanolone on drug abuse behavior during pregnancy in a clinical population. Adding this neurosteroid to our project represents a new focus in our research by investigating a possible neurobiological protective factor in smoking behavior. Considering the substantial role of allopregnanolone on drug abuse behavior in the animal literature, the knowledge gained from this project has the potential to directly influence and inform new postpartum smoking relapse prevention programs given that exogenous distribution of allopregnanolone has recently been proven to be safe in non-pregnant clinical populations. Third, utilizing the two clinical models (pregnancy and oral contraceptives) will allow us to better assess the independent effects of sex hormones on smoking-related symptomatology and nicotine response. While motivations for smoking may change dramatically during pregnancy for a variety of reasons (i.e. infant health, social norms), utilizing these two clinical models will allow us better focus on the relationship between sex hormones, smoking-related symptomatology and nicotine response by comparing the associations of sex hormones and study outcomes between clinical models.

22

to

THE APPROACH

PRELIMINARY STUDIES

Study #1: Impulsivity Varies by Menstrual Phase after Exposure to Nicotine. Goal: This cross-over study aimed to measure differences in nicotine response between follicular (F) and mid-luteal (ML) menstrual phases in a sample of female smokers between the ages of 18 and 40 (n=20). Results: After exposure to nicotine nasal spray, participants in the F phase became significantly more impulsive on the Immediate Memory Task computer program²⁴ compared to participants in the ML phase (Figure 2). *Relevance: Sex hormones appear to impact the level of impulsivity, such that higher levels of progesterone are associated*

[figure not shown]
with less impulsivity after exposure to nicotine.

Study #2: Changes in Estradiol/Progesterone (E2/P) Ratio is Associated with Changes in Craving.

Goal: This study aimed to assess the influence of the E2/P ratio on smoking-related symptoms of withdrawal (MNWS),²⁵ smoking urges (Brief-QSU),²⁶ and reinforcing effects of smoking (mCEQ)²⁷ using a within subject analysis in a sample of female smokers (n=50) with regular menstrual cycles between the ages of 18 and 40. Results: During ad libitum smoking, an increase in the E2/P ratio was associated with an increase in craving on two independent items of measurement: mCEQ (t=2.38, p=0.02) and MNWS (t=1.92, p=0.06). *Relevance: Changes in sex hormone levels are associated with changes in craving for cigarettes.*

Study #3: Smoking Satisfaction & Enjoyment Vary by Menstrual Phase during Ad Libitum Smoking.

Goal: The purpose of this cross-sectional study was to investigate the differences in reinforcing effects (mCEQ)²⁷ of smoking by menstrual phase and depressive symptoms in a sample of female subjects (n=39) who were classified into four groups: no depressive symptoms follicular phase (NDS-F), no depressive symptoms luteal phase (NDS-L), depressive symptoms follicular phase (DS-F) and depressive symptoms luteal phase (DS-L). Results: Smoking Satisfaction varied by menstrual phase in the NDS group but not in the SDS group (F-NDS: 5.2±0.5; L-NDS: 3.4±0.5; F-SDS: 4.5±0.4; L-SDS: 4.8±0.3; p=0.016; **Figure 3**) and a similar trend was observed within the Enjoyment subscale (F-NDS: 4.4±0.6; L-NDS: 1.7±0.6; F-SDS: 3.6±0.5; L-SDS: 2.9±0.5; p=0.089). *Relevance: Among those without depressive symptoms, sex hormones appear to impact the level of reinforcing effects of smoking, such that higher levels of progesterone are associated with less smoking satisfaction and less enjoyment.*

[figure not shown]
Study #4: Hormonal Contraceptive Use is Associated with Higher Levels of a Cigarette Biomarker.

Goal: This cross-sectional study aimed to measure differences in NNAL, a biomarker of carcinogen exposure to cigarette smoking, between three groups of adolescent smokers (ages 13 to 19): females on hormonal contraceptives (F-HC; n=33), females not on hormonal contraceptives (F-no HC; n=27) and males (M; n=40). Results: After controlling for cigarettes/day, F-HC had the highest levels of NNAL values compared to F-no HC and M (1.00±0.89 vs. 0.46±0.31 vs. 0.71±0.59; f value=4.90, p=0.010). *Relevance: Sex hormones appear to impact biomarker levels associated with the exposure to cigarette smoking.*

Study #5: Pharmacokinetics of Nicotine varies by Menstrual Phase in Women without Depressive

Symptoms. Goal: This cross-over study aimed to measure menstrual phase differences in pharmacokinetics after exposure to nicotine nasal spray within a sample of abstinent female smokers with regular menstrual cycles who either had depressive symptoms (n=23) or did not (n=24). Results: There was a significant interaction between depressive symptoms status and menstrual phase such that those without depressive symptoms had a significant menstrual phase difference in their maximum nicotine concentration levels (p=0.020; Figure 4). *Relevance: In women without depressive symptoms higher progesterone levels are associated with lower nicotine response*

Figure 4. Mean Plasma Nicotine Concentrations Following Nicotine Nasal Spray Use

Study #6: Age of Menarche Predicts Onset of Smoking but Perception of Maturity does not.

Goal: The goal of this retrospective study was to investigate the association of self-reported age of onset of daily smoking with self-reported age of menarche and perceived maturity level at age of menarche in a sample of female smokers (n=54) between the ages of 18 and 40. Results: Older age at menarche was associated with an older age at initiation of daily smoking (f-value=5.60, p-value=0.02). Perception of maturity was not significantly associated with smoking initiation (f-value=0.41, p=0.53). *Relevance: Menarche represents marked sex hormone fluctuations and instability; it may be that the fluctuating sex hormones impact smoking behavior more than the perception of these life changes.*

PROGRESS REPORT

For the past 20 years we have conducted research funded under NIDA grant R01-DA08075. This project's overall goal is to investigate the influence of ovarian hormones, both with and without the use of nicotine replacement therapy, on multiple outcomes: women's smoking behavior, relapse to smoking after a quit attempt, relapse-related factors including withdrawal symptoms, premenstrual symptoms, weight gain, caloric intake, negative mood, and nicotine response.

During the past funding period (May 2007 to October 2011), our findings were disseminated in eight peer-reviewed journal articles and 20 poster/oral presentations at local, national, and international scientific meetings (see Section 2.5 for Progress Report Publication List). As of February 2011, we have begun analyzing data from our completed pharmacokinetics subgroup. Based on these results we have two manuscripts in various stages of publication. These manuscripts will describe the menstrual phase differences in the changes in serum cortisol and nicotine levels after a nicotine challenge via nicotine nasal spray in a sample of 52 female smokers who have been abstinent for four days.

Menstrual Phase & Depressive Symptoms in Acute Smoking Abstinence (Continuation Grant R01-DA08075) *Project Period* reported on includes May 2007 to October 2011. This project's *specific aims* are: Aim 1: Determine the effect of depressive symptoms, alone and in concert with ovarian hormones (i.e. menstrual phase: follicular versus luteal) on withdrawal symptoms, nicotine craving, smoking urges, premenstrual symptoms and cortisol levels (measuring stress response) during acute smoking abstinence; Aim 2: Determine if depressive symptoms and menstrual phase moderate nicotine response following acute smoking abstinence. *Study Design*: This study utilized a randomized cross-over design to compare within subject effects of menstrual phase and between subject effects of depressive symptoms. A convenience sample is stratified by depressive symptoms, then randomized to testing order (follicular phase then luteal phase or vice versa). Each participant then completed two six-day testing sessions including two days of ad libitum smoking followed by four days of smoking abstinence. During these testing sessions, participants attended daily clinic visits to biochemically verify smoking status, collect blood samples of measurement of sex hormones and complete self-reported items assessing mood and withdrawal symptoms. Participants also completed two nicotine lab exposure sessions during alternate menstrual phases. *Summary*: As described in the Preliminary Results Section, our previous work demonstrates not only our expertise in studying the hormonal influence on smoking behavior in women, but also the importance of this work. As detailed above (Section D.1) our most recent work has provided additional evidence for a relationship between sex hormones and drug abuse behaviors. Specifically we have shown higher levels of progesterone appear to be associated with blunted levels of impulsivity, less favorable responses to nicotine, and changes in levels of craving. *New Direction*: We are proposing to continue our exploration of the possible causal mechanisms of sex hormones on smoking-related symptomatology and nicotine response in pregnant women. During pregnancy progesterone, allopregnanolone and estradiol increase dramatically. This will provide us with an ideal clinical model to further investigate the relationship between sex hormones and smoking behavior, as well as fill a gap in the current body of literature and potentially provide new information and direction to improve smoking cessation rates during pregnancy. Our proposed study is further strengthened and innovative due to the inclusion of a more controlled study of sex hormone effects via the clinical model of oral contraceptives.

RESEARCH PLAN

Overview. Using two clinical models – pregnancy (Sample 1) and oral contraceptives (OC; Sample 2) – we aim to (1) examine the association between levels of progesterone (Prog), allopregnanolone (Allo) and the estradiol/progesterone (E2/P) ratios with smoking-related symptomatology during ad libitum smoking, and (2) determine the association between Prog, Allo, and E2/P with the changes in smoking-related symptomatology and response to nicotine following overnight abstinence. Sample 1 will enroll approximately 112 pregnant women to ensure a final sample size of 84 participants to participate in a cross-sectional study at two time points: 12 weeks to 22 weeks gestation (n=42) and 32 to 37 weeks gestation (n=42). Sample 2 will enroll approximately 78 OC users to ensure a final sample size of 52 participants in a randomized cross-over, double-blind study design to complete testing periods during “low” and “high” dose levels of exogenous progesterone with a consistent dose of exogenous estrogen. All participants will complete identical data collection procedures including providing saliva (cortisol to measure stress), urine (cotinine and 3-Hydroxycotinine to measure nicotine exposure, and medication compliance), and blood (progesterone, allopregnanolone, estradiol, and nicotine) samples, as well as ecological momentary assessments (EMA) daily for seven-days. Participants will also complete a three-hour smoking lab session (with the first morning

cigarette) and a four and a half-hour nicotine exposure lab session (after at least 13 hours of overnight abstinence). These sessions will contain a nicotine challenge via nicotine nasal spray or smoking topography with timed-series of physiological, subjective and behavioral responses.

Recruitment. Our primary recruitment strategy for both study samples is via two clinical sites: (1) Obstetrics & Gynecology Clinic at Hennepin County Medical Center (HCMC), the fourth largest hospital in Minnesota and is a safety net facility for low-income, uninsured and other vulnerable populations (see Section 2.14 for letter of support) and (2) Fairview Riverside Women's Clinic at Fairview University Medical Center (FUMC; see Section 2.14 for letter of support). Among these two clinics an estimated 4,900 infants are born each year. Given an estimated 23% of women of childbearing age currently smoke about 50% quit smoking during pregnancy,⁷ about 15% of pregnant women experience a pregnancy-related complication²⁸ and an estimated 15% are using psychotropic medications,²⁹ we roughly estimate approximately 407 pregnant women will meet our inclusion/exclusion criteria (details described below) for Sample 1 each year (4,900 infant births/year x 23% smoking prevalence x 50% smoking cessation x 85% no pregnancy complications x 85% no psychotropic medications). We will also recruit non-pregnant women who are on oral contraceptives from these two clinical sites. Based on preliminary results from our current study, we estimate 40% of women who smoke are oral contraceptive users and 15% are currently being treated for psychiatric problems. At each clinical site we will post flyers and business cards in the waiting and exam rooms at the Hennepin County Medical Center Obstetrics & Gynecology Clinic, and the Fairview Riverside Women's Clinic. These flyers and business cards will instruct potential participants to call study staff for more information.

In addition to recruiting at clinical sites we will also use two additional recruitment methods. The first is via the *Minnesota Academy of Family Physicians Research Network*. Approximately 80 MAFP members practice in the Minneapolis/St. Paul metro and greater surrounding area. The overall clinical populations within this network include 64% women who are White (82%), Asian (8%), Black (6%) and other/unknown (14%). Since MAFP physicians often have individual practices and are familiar with conducting clinical research, they will refer potentially eligible participants to our research study (see Section 2.14 for letter of support). The second recruitment method is *advertising in the mainstream media*. While this type of recruitment can be challenging, our team has been successful with this form of recruitment with both non-pregnant and pregnant women. For example, our current study recruiting non-pregnant women between the ages of 18-40 has had success with Facebook advertising. Specifically, over the past six months we have advertised on Facebook resulting in 4,121 clicks to our website, an estimated 130 phone calls to our clinic and an enrollment of 23 participants (~4 participants/month). Similarly, [name] (Co-I) ongoing study on pregnancy and depression recently sent out an email to the local newspapers listserv. This email was opened 21,700 times, resulting in 338 clicks to the study website. A total of 109 participants were enrolled into the study, the majority of which were recruited directly from this single email. In addition to these two examples, we regularly use television, radio, mailings, and other internet sources to identify study participants with similar success.

Study Samples. While all participants in Sample 1 (Pregnant Women) and Sample 2 (Oral Contraceptive Users) complete identical data collection procedures, there are some differences in inclusion/exclusion criteria, timing of the testing periods and follow-up procedures. Those differences are described here and in Table 1.

Sample 1 – Participants. To meet recruitment goals, we will aim to enroll 38 pregnant women per year (~3-4 women/month). Inclusion criteria: females 18-35 years old, in stable physical/mental health with confirmed pregnancy, self-reports smoking ≥ 5 cigarettes/day for the past year, has established prenatal care, single gestation, either 12-22 or 32-37 weeks gestation, English fluency, and able to provide informed consent. Exclusion criteria: use of psychotropic medications or illicit drugs with the exception of marijuana use ≤ 2 times per month and a willingness to abstain from marijuana during the testing period, current use of other types of tobacco or nicotine, or pregnancy complications (i.e. gestational diabetes, known congenital anomaly, fetal growth restriction, pregnancy hypertension and history of >2 miscarriages). Finally, participants will not be eligible to participate in the study at more than one time point (i.e. 12-22 and 32-37 weeks gestation) due to the potential ethical issues associated with administering nicotine nasal spray multiple times during pregnancy and/or unintended encouragement to continue smoking to be eligible to participate again.

Sample 1 - Timing of Testing Period. The testing period will occur during either 12-22 or 32-37 weeks gestation (participants complete one testing period only). These gestational weeks were selected to capitalize on the expected variability in sex hormones (e.g. 12-22 weeks gestation expected progesterone values are **19.5** to 89.4 ng/mL and 32-37 weeks gestation expected progesterone values are 48.4 to 200.0 ng/mL).²⁰ We will not be assessing the first trimester (due to the high risk for miscarriage and delay of initial prenatal care) nor late third trimester (due to the possibility of early delivery).

Sample 1 - Follow-up. After completing the testing period (described below) participants will receive smoking cessation behavioral counseling, self-help materials, advice for pharmacotherapy (and a prescription, if necessary) per the discretion of the study physician ([name], PI) and referrals to smoking cessation programs. Additional weekly phone counseling will be offered.

Sample 2 - Participants. To meet recruitment goals, we will aim to enroll 27 OC users per year (~3 women/month).

Inclusion criteria: females 18-35 years old, in stable physical/mental health, self-reports currently smoking ≥ 5 cigarettes/day for at least the past year, using OC for at least the past three months without complication, willing to switch to study supplied OC, English fluency, and able to provide informed consent. **Exclusion criteria:** use of psychotropic medications or illicit drugs with the exception of marijuana use ≤ 2 times per month and a willingness to abstain from marijuana during the testing periods, current use of other types of tobacco or nicotine, current breast feeding, planning to become pregnant within the next three months, current use of finasteroid (propecia), efavirenz, red clover, ketoconazole and other drugs that are CYP3A4 inhibitors, and conditions contraindicated to progesterone treatment (including, but not limited to, thrombophlebitis, deep vein thrombosis, pulmonary embolus, clotting or bleeding disorders, heart disease, diabetes, history of stroke, allergy to peanuts, hypersensitive to progesterone and liver dysfunction).

[figure not shown]
Sample 2 - Timing of Testing Period. As in Sample 1, the timing of the testing period has been selected to maximize the variability in sex hormones by OC use. Participants will be randomly assigned to order to complete two testing periods: “low” dose progesterone versus “high” dose progesterone. To obtain these values participants will be supplied with Tri-Sprintec (Barr Laboratories Inc.; Appendix A) and generic Prometrium (Teva Pharmaceuticals USA Inc/Appendix A). The “low” dose progesterone is seven days of placebo Tri-sprintec + placebo generic Prometrium twice a day (7AM and 7PM). The “high” progesterone dose is seven days of placebo Tri-Sprintec + 200mg of generic Prometrium twice a day (7AM and 7PM).

The Wednesday after their Screening Visit (described below), participants will begin taking the Tri-Sprintec medication.

Table 1. Methodology Comparison of the Two Study Samples

	Sample 1 Pregnant Women (n=84)	Sample 2 Oral Contraceptive (OC) Users (n=52)
Inclusion Criteria	
 • 18-35 years old • Stable physical/mental health • ≥ 5 cigarettes/day for ≥ 1 year • 16-20 or 32-36 weeks gestation • Established prenatal care • Single gestation • English fluency • Able to provide informed consent 	
 • 18-35 years old • Stable physical/mental health • ≥ 5 cigarettes/day for ≥ 1 year • Current OC user willing to switch to study supplied OC • English fluency • Able to provide informed consent
Exclusion Criteria	
 • Use of psychotropic medication, illicit drugs or other types of tobacco/nicotine • Pregnancy complications 	
 • Use of psychotropic medication, illicit drugs or other types of tobacco/nicotine • Current breastfeeding • Planning to become pregnant within next 3 months • Conditions or medications contraindicated to progesterone
Timing of Testing Period	One eight-day testing period completed, schedule per participant availability: 
 • 16-20 weeks gestation, or • 32-36 weeks gestation 	Two eight-day testing periods completed, order randomly assigned: 
 • Low dose progesterone, and • High dose progesterone
Clinic Visits	
 • Screening Visit • 4 follow-up visits 	
 • Screening Visit • 6 follow-up visits (4 visits during each testing session)
Follow-up	
 • Smoking cessation counseling offered. 	
 • Participants return to ad lib smoking for six weeks then completing identical testing session in opposite phase (i.e. low or high dose progesterone). • Smoking cessation counseling offered.

Figure 5. Expected Sex Hormone Values in Oral Contraceptive Users by Testing Period

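### Sample 2 is meant to be non-pregnant, but the protocol text schedules no pregnancy test before progesterone and nicotine spray are given; a Day 0 urine test is a cheap, minor safety improvement

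*Combined protocol and SAP*

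**What the plan says.** All references are to the combined protocol and SAP.

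- **Who Sample 2 is.** Recruitment: "We will also recruit non-pregnant women who are on oral contraceptives from these two clinical sites".
- **Eligibility.** Sample 2 - Participants requires "using OC for at least the past three months without complication". The pregnancy-related exclusions are "current breast feeding, planning to become pregnant within the next three months", and Table 1 repeats them in short form. A further exclusion is open-ended: "conditions contraindicated to progesterone treatment (including, but not limited to, thrombophlebitis", followed by other conditions. Current pregnancy is not named.
- **Screening visit (Data Collection Procedures).** It includes medical history, vital signs, carbon monoxide and the suicidality scale. AST and ALT are the only screening blood tests for Sample 2.
- **Day 0.** Urine is taken for nicotine exposure and blood for sex hormones. The first capsules of progesterone or placebo are handed out at this visit, to be started at 7PM.
- **Table 2.** There is no pregnancy-test row.
- **Dosing.** Prometrium 200 mg or placebo is taken twice a day for seven days, active in one testing period and placebo in the other. Nicotine spray is practised on Day 6 and given on Day 8 of both periods.

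**The concern.** The plan asserts a status, non-pregnant, and provides no step that would verify it. Asking about history, or applying the contraindication clause, works only if the woman knows she is pregnant. A woman with an early, unrecognised pregnancy would answer truthfully and be enrolled.

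What is at stake is participant safety and the basis on which she takes part. Sample 1 women receive the spray with a confirmed pregnancy and established prenatal care. A Sample 2 woman who is unknowingly pregnant would have neither, and she would also take a week of active progesterone. The trial's conclusions are hardly at stake: an isolated pregnancy would disturb that woman's hormone values and little else.

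**Working it through.** The plan states no figure on this point, so the check is a reading of the visits followed by simple arithmetic on exposure and timing.

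**1. Could any scheduled step detect an unrecognised pregnancy?**

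- Medical history: known pregnancy only.
- Contraindication clause: known pregnancy only.
- AST/ALT: not a pregnancy test.
- Urine on Days 0, 6 and 8: cotinine, 3-hydroxycotinine and, on Days 6 and 8, riboflavin colour for compliance.
- Serum progesterone and estradiol: the Day 0 draw precedes the first capsule, so a raised value could hint at pregnancy. Study Measures presents these as independent variables to be averaged over the testing period. No review before dosing and no action threshold is given.

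None of these is a scheduled means of detection.

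**2. What would such a woman receive?**

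- Prometrium: 7 days × 2 doses × 200 mg = 14 doses, 2,800 mg, in one period only. If taken from 7PM on Day 0 through 7AM on Day 8, this becomes 16 doses, 3,200 mg.
- Spray: 4 sprays × 0.5 mg = 2 mg per dose. The Day 8 text supports more than one reading of the number of doses: one (2 mg), two (4 mg) or three (6 mg). Over two periods that is 4, 8 or 12 mg, plus two Day 6 practices of unstated amount.
- Tri-Sprintec: three weeks before the first testing period, then placebo tablets in both testing weeks. She has already used an oral contraceptive for at least three months, so this is not a new class of exposure.

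**3. Where should a test sit?** Tri-Sprintec starts on the Wednesday after screening, taken as 1 to 7 days later, and runs for 21 days before the first testing period.

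- First Day 0: 1 + 21 = 22 to 7 + 21 = 28 days after screening.
- First Day 8: 30 to 36 days.
- Second Day 0 with the three-week gap in Sample 2 - Follow-up: 30 + 21 = 51 to 36 + 21 = 57 days.
- Second Day 0 with the six-week gap in Table 1: 30 + 42 = 72 to 36 + 42 = 78 days.

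A screening result would be three to four weeks old at the first dosing week and seven to eleven weeks old at the second. A test at each Day 0 precedes the Prometrium, the Day 6 practice and the Day 8 spray of that period.

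**4. Number of tests** (78 enrolled and 52 final, from Sample Size & Power Analysis): 78 + 52 = 130. If all 78 reached the second period: 2 × 78 = 156.

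**The case against.** The case against giving this much weight is substantial, and most of it stands.

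- **The absence is shown only for the text available.** The protocol refers to appendices and to other sections, and the consent form was not available. A pregnancy test could be described there. This stands and limits the claim.
- **The event should be rare.** Women must be established contraceptive users, and planned pregnancy is excluded. This stands. The documents give no pregnancy rate, so no probability is offered here.
- **No harm is documented.** A reader might infer that the plan exposes a fetus to a known hazard. The documents do not say so for progesterone or the contraceptive. The Innovation section states "Delivery of exogenous progesterone during the third trimester is an accepted treatment for pre-term delivery prevention". That concerns the third trimester and does not settle early pregnancy either way, but it gives no ground for claiming harm.
- **The spray is given deliberately to pregnant women in Sample 1.** The Day 8 text reports an ethics opinion finding no major issue with this dose. It also cites a study in which 11 doses lowered maternal nicotine exposure relative to smoking. Sample 2 women already smoke and abstain overnight before the session, so no net increase in nicotine is shown.
- **The one-time-point rule belongs to Sample 1.** A reader might infer that the plan would breach its own rule that "participants will not be eligible to participate in the study at more than one time point", justified as "due to the potential ethical issues associated with administering nicotine nasal spray multiple times during pregnancy and/or unintended encouragement to continue smoking". That rule is written for the two gestational windows of Sample 1, and part of its reason is not to encourage smoking. Nothing extends it to Sample 2; it is an analogy only. The first-trimester restriction helps no more: "We will not be assessing the first trimester (due to the high risk for miscarriage and delay of initial prenatal care" gives reasons unrelated to drug or spray exposure.

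None of this supplies a means of finding an unrecognised pregnancy before dosing, so the narrow point survives.

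**Conclusion.** The point holds as a minor safety improvement. In the protocol text available, Sample 2 is described as non-pregnant, current pregnancy is not a named exclusion, and no visit includes a pregnancy test. An unrecognised pregnancy could therefore pass through 14 doses (2,800 mg) of Prometrium in one week and nicotine spray in two testing periods.

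This rests on three assumptions: that the appendices and consent form do not already require a test, that Day 0 hormone results are not reviewed before dosing, and that the schedule is followed as written. Naming pregnancy as an exclusion is a wording repair, since a known pregnancy could already be removed. The test is the substance. The effect on the trial's results is negligible.

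**What to change.** Unless the appendices, consent form or operating procedures already cover it:

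1. List current pregnancy as an exclusion in Sample 2 - Participants and in Table 1.
2. Require a negative urine pregnancy test at Day 0 of each testing period, on the urine already collected, before capsules are supplied.
3. Add the row to Table 2, marked Sample 2 only.
4. State that no study drug or nicotine spray is given after a positive result.

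The cost is a short amendment and about 130 inexpensive tests, at most 156. There is no added visit or specimen, and the downside is the test cost and the possible loss of a participant. A further test at screening, before Tri-Sprintec, is optional. It would add 78 tests (130 + 78 = 208, at most 156 + 78 = 234) and is not needed to protect against the Prometrium or spray exposure.
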